## 5.0 Study Procedures

## 5.1 Study Design

**Group Intervention.** Veterans will participate in a LC-CR group (75 minutes 1x/week for a total of 16 sessions) via the HIPAA-compliant telehealth platform VA Video Connect (VVC) in accordance with the Office of Connected Care (OCC)'s best telehealth practices. VA WebEx will be available as an approved back-up telehealth platform in the event of VVC technical difficulties.

The intervention will be delivered in two modules consisting of 8 sessions each (16 sessions total):

**Module 1:** The first 8 sessions of the treatment will focus on skill based coping strategies to target more immediate symptoms and Long-COVID related issues as part of the recovery process.

**Module 2:** The second 8 sessions will focus on more long-term recovery and creating a meaningful and purposeful future.

Sessions will be co-facilitated by [name] and another co-therapist. [name] will be the co-therapist for Module 1 of therapy (first 8 sessions) and [name] will be the co-therapist for Module 2 of therapy (second 8 sessions).

**Timeline:** (See **GANTT chart**) For the first 3 months we will complete the needs assessment interviews. In months 4-7, we will revise the psychotherapy workbook and therapist manual *and will consult with stakeholders monthly for input on revisions throughout our piloting phases*. In months 18-24, we will develop and submit a RR&D Merit grant application for an RCT to test the treatment.

Project dates: 10/1/22- 9/30/24	Year 1				Year 2			
	Q1	Q2	Q3	Q4	Q1	Q2	Q3	Q4
Activity	October - December (2022)	January-March (2023)	April-June (2023)	July-September (2023)	October-December (2023)	January-March (2024)	April-June (2024)	July-September (2024)
IRB								
Train RA and other startup activities								
Complete PACS needs assessment								
Analyze needs assessment results								
Finish developing psychotherapy materials and therapist manual								
Consult with stakeholders on proposed intervention and revise materials								
Run first set of pilot group								
Revise treatment based on trial participants and stakeholder feedback								
Run second set of pilot groups								
Present findings								
manuscript preparation								
Merit preparation/sSubmission								

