## **5.5 Study Evaluations**

**Clinical Assessments and Schedule.** Patients will have been screened/diagnosed as a part of their local VAMC's Long-COVID Clinical Center. Interested eligible participants will enroll and undergo assessments at pre (consent & baseline), immediately post module 1 of therapy (after first 8 sessions) and immediately post module 2 of therapy (after second 8 sessions) via either in person, over the phone, or via HIPAA-compliant web platform VA Video Connect (VVC) (with Audacity audio recording software) with VA WebEx as a viable backup depending on the participant's preference/availability.

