MINI Mental State Examination (MMSE)	Cognitive Function	Consent & baseline	1
The World Health Organization Disability Assessment Schedule, 2nd Version (WHODAS 2.0)	Functional Status as relates to health (primary outcome)	Consent & baseline, post- Mod 1, Post Mod 2,	3
Suicide Behaviors Questionnaire- Revised (SBQ-R)	Suicidal Risk/Behavior	Consent & baseline, post- Mod 1, Post Mod 2,	3
Measure of Current Status (MOCS)	Resilience	Consent & baseline, post- Mod 1, Post Mod 2,	3
The Quality of Life Scale (QOLS)	Quality of Life	Consent & baseline, post- Mod 1, Post Mod 2,	3
Future Self-Continuity Questionnaire, (FSCQ)	Identity Concerns	Consent & baseline, post- Mod 1, Post Mod 2,	3
GAD-7 Anxiety	Anxiety	Consent & baseline, post- Mod 1, Post Mod 2,	3
Patient Health Questionnaire- 9 (PHQ-9)	Depression	Consent & baseline, post- Mod 1, Post Mod 2,	3
COVID-19 Yorkshire Rehabilitation Scale (C19-YRS)	Long COVID Symptom severity	Consent & baseline, post- Mod 1, Post Mod 2,	3
Questionnaire about the Process of Recovery (QPR)	Progress through Recovery Process	Consent & baseline, post- Mod 1, Post Mod 2,	3

**Feasibility and acceptability metrics.** Feasibility will be tracked through 1) implementation ease - tracking the hours clinicians spend in preparation, delivery, and supervision with a target of 100 hours/ cycle (5 hours per group). 2) recruitment - tracking referrals and 3) attendance/retention - tracking the sessions Veterans attend. Our criteria for retention will be “adequate” if 60% attend at least 5 of the first 8 sessions (Module 1), 5 of the second 8 sessions (Module 2), and 10 of the total 16 sessions (Module 1 + Module 2). A similar strategy will be used for recruitment rates, with feasibility deemed “adequate” if at least 60% of Veterans approached for participation in the study agree. At the end of each session, we will ask veterans the following questions: “What did you like about this session?” “What did you not like about this session?” “Do you have any suggestions for improvement?” to gauge acceptability, feasibility, and appropriateness of each session.

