Veterans will complete the AIM, IAM and FIM ( Weiner et al., 2017) prior to and after completion of the program. These are four-item measures of implementation outcomes (acceptability and feasibility of intervention and intervention appropriateness) that are often considered “leading indicators” of implementation success (Proctor et al., 2011). We will also track homework adherence by percent complete. Lastly, upon completion of all LCCR sessions we will ask the veterans’ additional questions to obtain *participants’ feedback on the group*. Responses will be de-identified and analyzed for future development and implementation purposes.

Test /Procedure:	Outcome	When:	# of times:
Acceptability of Intervention Measure (AIM) Weiner et al., 2017)	How acceptable or satisfactory is the LC-CR group is to Veterans	Pre-treatment, Post-treatment (Mod 1), Post treatment (Mod 2)	3
Intervention Appropriateness Measure (IAM) Weiner et al., 2017)	How is the perceived fit, relevance, or compatibility of LC-CR to Veterans	Pre-treatment, Post-treatment (Mod 1), Post treatment (Mod 2)	3
Feasibility of Intervention Measure (FIM) Weiner et al., 2017)	How easy is it to participate in LC-CR	Pre-treatment, Post-treatment (Mod 1), Post treatment (Mod 2)	3
Qualitative Interviews	Acceptability, Feasibility, and Appropriateness of Intervention to help identify other needed implementation strategies for future dissemination	Post-treatment (Mod 2)	1

**5.5.1 EMA Protocol (to be carried out at Minneapolis VA by [name] team):** Participants who opt-in to the optional EMA component of the study during the consent process will be scheduled to receive three different week-long bursts of daily surveys (one at baseline, mid-treatment, and end of treatment). Each survey will contain approximately 20 questions and will be delivered at the end of the day (at a personalized time). They are expected to take approximately 3 minutes to complete. The surveys do not contain any intervention component. Participants will receive links to these questionnaires via text message.

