## 5.6 Data Analysis

All data will be de-identified before it is entered into a redcap database at the JJPVA over the intranet.

**5a. Statistical approach.** Descriptive statistics will be calculated, and outcome measures will be compared across the time points using repeated-measures mixed models. Data will be used to examine acceptability and feasibility, and iteratively improve the treatment. Then, we will apply for a RR&D VA Merit to determine efficacy of LC-CR in an RCT.

**5b. LC-CR Fidelity Measure.** Our research team (Drs. [name] and [name]) have experience establishing fidelity of psychosocial interventions. After the first pilot, an adherence scale will be created to assess 1) general LC-CR requirements, 2) session specific requirements, and 3) general group psychotherapy requirements.

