**Developing an Integrative, Recovery Based, Post-Acute COVID-19 Syndrome (PACS)
Psychotherapeutic Intervention, “PACS Coping and Recovery”**

Funding Agency: Rehabilitation Research and Development Service (RR&D) Small Projects in Rehabilitation Research (SPiRE).

NCT05453201

June 1, 2024

JJPVAMC

PI: [name]

Co-I: [name]

Co-I: [name]

Co-I: [name]

All statistical analyses were conducted using the RStudio (version 4.4.2). Item-level missingness (< 0.5% item-level observations) was handled with participant-mean imputation. Little's (1988) missing completely at random (MCAR) test was not significant ($p > .05$) indicating that the data were missing at random. Paired-sample t-tests were used to examine changes in primary and secondary outcomes from pre- to post-treatment. Paired Wilcoxon tests were used when the Shapiro-Wilk test was significant ($p < .05$). The significance level was set at $p < .05$ for all analyses.

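### The SAP replaces the protocol's three-visit mixed models with pre/post paired tests without giving a reason, so one scheduled visit goes unanalysed; any bias from missed final visits is secondary and cannot be determined from the documents

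*SAP*

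**What the plan says.** Protocol section 5.6 (5a) says that "outcome measures will be compared across the time points using repeated-measures mixed models". It gives no covariance structure and no further detail.

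Protocol section 5.5 sets three assessments: before treatment, right after Module 1 and right after Module 2. Its schedule table lists nine outcome scales at all three. They are WHODAS 2.0 (marked as the primary outcome), SBQ-R, MOCS, QOLS, FSCQ, GAD-7, PHQ-9, C19-YRS and QPR. The modules differ in content. Section 5.1 says of Module 1 that "The first 8 sessions of the treatment will focus on skill based coping strategies", and gives Module 2 to longer-term recovery.

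The SAP is one paragraph in the past tense. Its outcome analysis is: "Paired-sample t-tests were used to examine changes in primary and secondary outcomes from pre- to post-treatment". Paired Wilcoxon tests take over when a Shapiro-Wilk test is significant. On missing data it says: "Item-level missingness (< 0.5% item-level observations) was handled with participant-mean imputation". It then reports a non-significant Little's test as "indicating that the data were missing at random". It mentions no mixed model, no analysis of the visit after Module 1 and no rule for a missed visit. It does not say which visit counts as post-treatment.

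**The concern.** The method in the protocol and the method in the SAP are different analyses, and no reason is given. The SAP wording already reports a test result, so the switch was written down with data in hand. A reader needs to know why it was made.

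Two things are at stake.

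- **Loss of a scheduled visit.** This holds whatever the amount of missing data. The study cannot show whether change came during Module 1 or Module 2, although the modules have different content and the results are meant to shape a later RCT.
- **Possible bias.** A paired test uses only Veterans with both scores. Protocol section 5.7 foresees Veterans stopping treatment. If some of them also have no final score, and this relates to how they were doing, the completers' change is not the change in all who started. A mixed model can use a leaver's earlier scores; the paired test cannot.

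The overall goal in section 3.0 is acceptability and feasibility. However, Aim 2 is to identify possible benefits, section 7a says initial efficacy is being evaluated, and the paired tests are the only outcome analysis in the SAP.

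**Working it through.** Neither document states a power, effect size, SD, correlation or dropout rate for these tests, so there is no planned figure to reproduce.

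**1. Scores left out (inputs from protocol sections 5.2 and 5.5).** 9 scales x 3 visits x up to 36 Veterans = 972 scheduled scores. A pre/post test uses two visits, so 9 x 36 = 324, one third, enter no SAP analysis. The implementation-measure table uses a post-treatment label for both later visits, while the text above it says "prior to and after completion of the program". The natural reading is the visit after Module 2. On either reading one visit is left out.

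**2. What the unused visit could show.** With all 36 Veterans, the 95% CI half-width for one module's change, in baseline SDs, is t(35) x sqrt(2(1 - r)/36), with t(35) = 2.030.

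- r = 0.5: 2.030 x sqrt(1/36) = 0.338
- r = 0.7: 2.030 x sqrt(0.6/36) = 0.262

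**3. What the SAP's < 0.5% can tell us.** If the denominator is every scheduled item, one wholly missed visit is about 1/(3 x 36) = 1/108 = 0.93%. Baseline also carries the 11-question MMSE, so a later visit is slightly less. The scales whose item counts the protocol states directly (FSCQ 10, QPR 22, C19-YRS 22, PHQ-9 9) give at least 63 items per visit. The share is then at least 63/(36 x (3 x 63 + 11)) = 63/7200 = 0.875%, still above 0.5%, and larger if fewer than 36 enrolled. On that denominator no visit was wholly missed. If the denominator is completed questionnaires only, the figure says nothing about missed visits. The SAP does not say which.

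**4. Bias if dropout depends on observed early change.** Assumptions, not from the documents: equal SDs of 1; equal correlation r of 0.5-0.7 between visits; the log-odds of a missing final score change by 0.5-1.0 per baseline SD of early change, in either direction. The slope of final change on early change is (1 - r)/(2(1 - r)) = 0.5. So bias = 0.5 x (mean early change among those with a final score, minus the overall mean). This was integrated numerically, with the intercept set to give each retention rate.

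| Final scores present | Absolute bias of paired change (SD) |
|---|---|
| 95% | 0.007-0.024 |
| 90% | 0.015-0.045 |
| 80% | 0.029-0.087 |
| 60% | 0.058-0.166 |

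The sign follows who leaves. Bias is zero with complete data or random dropout.

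The three-visit model was simulated at N = 36 (6,000 replicates per scenario). Its residual bias is:

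- within 0.005 SD if all leavers have the visit after Module 1;
- 0.01-0.02 SD (80%) and 0.01-0.03 SD (60%) if half lack it;
- 0.02-0.05 SD (80%) and 0.04-0.09 SD (60%) if all lack it.

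**5. Bias if dropout depends on the unseen final score.** Same settings, with missingness driven by the final change. The factor 0.5 disappears, so the paired bias doubles. The model column is a large-sample calculation in which every leaver has the visit after Module 1.

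| Final scores present | Paired (SD) | Three-visit model (SD) |
|---|---|---|
| 80% | 0.06-0.17 | 0.04-0.12 |
| 60% | 0.12-0.33 | 0.08-0.23 |

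The model removes only about 30%.

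**The case against.** The strongest reply is that the bias is hypothetical. No document shows a missed final assessment, and the correlations, dropout strengths and retention rates above are assumed. The 60% in section 5.5 is a session-attendance criterion, not an assessment-completion rate, and stopping treatment is not the same as missing an assessment. At 90% retention or better the bias is trivial. With complete data the baseline to post-Module 2 estimate is the same under either method. In an uncontrolled pilot neither analysis can attribute change to the therapy. All of this stands, and it is why bias is the secondary point. It does not explain the departure or the unused visit.

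It can also be said that counts of pairs are results, which a SAP need not hold. That is fair: they belong in the report.

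Three stronger readings are tempting but not supported:

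- **That the reported changes are inflated towards benefit.** The direction depends on who left, and nobody may have.
- **That the tests were chosen because of the results.** The past tense shows the text was written with data in hand. It does not show when or why the method was chosen.
- **That the mixed model would cure any dropout problem.** It relies on missing at random. It corrects only partly for leavers without the visit after Module 1. If missingness depends on the unseen final score, it fails in large part even for leavers who have that visit.

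**Conclusion.** The departure is real and unexplained, and it leaves one of three scheduled visits, for the primary outcome and eight other scales, outside every analysis in the SAP. That part rests on the text alone.

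The bias is conditional. Under the assumptions above, with dropout tied to early change, it is small unless about a fifth or more of final scores are missing. It is larger, and only modestly reduced by the model, if dropout follows the unseen final score. The actual bias is unknown and may be zero.

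Little's test does not settle the matter. A non-significant result in at most 36 people does not establish the mechanism. The test addresses missing completely at random, yet the SAP concludes missing at random. It is also not said whether whole missed visits were included.

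**What to change.** - Make the protocol's mixed model the main analysis, with all three visits and every Veteran who has a baseline. Report the baseline to post-Module 2 and baseline to post-Module 1 contrasts with 95% CIs, WHODAS 2.0 first. The protocol leaves the model form open, so the SAP should state it.
- Keep the paired tests as a supplementary analysis, labelled as a departure from the protocol, with the reason.
- State that the model assumes missing at random, and do not rest this on Little's test. If any final visit was missed, add a simple sensitivity analysis, such as a delta shift of the missing final scores. The paired test does not serve this purpose.
- Name the post-treatment visit. In the results, give the number assessed at each visit and the denominator of the < 0.5% figure.

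The cost is SAP wording and a minor re-analysis of data from visits already scheduled. The estimate may move in either direction, or not at all if no final visit was missed.
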